Participants will also be asked to complete the Multidimensional Fatigue inventory (MFI)[18], the Pittsburgh Sleep Quality Index (PSQI) [19], the perceived stress scale (PSS)[20], the Inventory of Depressive Symptomalogy-Self Reported (IDS-SR)[21], the PROMIS Fatigue Short form [28], the MOS-item Short-Form health survey (SF-36)(25) and the Godin Leisure-Time Exercise Questionnaire (GLTEQ)(26) to assess levels of fatigue, sleep, stress, and depression at the above time points. These surveys take approximately 15 minutes to complete. Patients who are simultaneously enrolled on the Fatique in Breast Cancer Patients Undergoing Treatment (IRB00028295) may have survey visit assessments completed prior to baseline visit, as they are completing the same assessments for both studies. These surveys will be used for data purposes in lieu of having the patient complete the same paperwork twice. At each visit, patients will be asked to rate their fatigue level and breast pain on a scale of 0-10, 0 being none and 10 being extreme. They will be asked to rate how happy they are with the look of their breast on a scale of 0-10, 0 being not happy and 10 very happy. They will be asked to rate how different their radiated breast is from their non-radiated breast on a scale of 0 - 10, 0 being no difference and 10 being completely different. The patient's self-report of fatigue at these visits will be used to assess the grade of their fatigue. In addition, patients will complete the LENT SOMA [27] scale patient questionnaire at all study timepoints to address pain within the breast. The objective LENT SOMA questionnaire Part 3 will be completed by a study clinician or trained nurse at each visit after baseline.

Blood will be drawn under fasting conditions at visits corresponding to cutaneous toxicity assessments. The blood will be analyzed for inflammatory markers (tumor necrosis factor (TNF)-alpha, soluble TNF receptor 2 (sTNFR2), interleukin (IL)-6, IL-1ra, and C - reactive protein (CRP) as well as genetic factors to determine if they are associated with development of cutaneous toxicity.

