#### **Primary Outcome Measure:**

- Cutaneous Toxicity Rate Cutaneous toxicity rate will be assessed by the National Cancer Institute Common Toxicity Criteria (NCI-CTC) v 3. grading scale.
- 1. Rate of 20% or greater increase in arm lymphedema (compared to baseline arm measurements) will be assessed Among breast cancer patients receiving regional nodal irradiation
- 2. Rate of Grade 3 brachial plexopathy will be assessed among breast cancer patients receiving regional nodal irradiation by RTOG and LENT/SOMA scales

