### Monitoring Plan for Severe Adverse Events:

We hypothesize that a maximum of 20% of patients might experience severe acute skin side effects defined as NCI-CTC Grade 3. This corresponds to symptoms interfering with activities of daily life. A Data Safety and Monitoring Board (DSMB) will monitor patient outcomes and suspend the protocol in the event that more than 16 of 80 patients demonstrate severe acute skin toxicity. During the study, the patients will be monitored continuously throughout the study such that if at any time during the study the upper limit of the number of patients developing Grade 3 toxicity exceed what is listed in the table below, the trial will be discontinued. With a 10% dropout rate, a total sample size of 83 patients was calculated to effectively test our hypothesis. For patients not requiring regional nodal irradiation, we will only collect adverse events related to skin toxicity, lung toxicity and heart toxicity. We will not report grade 1-2 radiation dermatitis as adverse events because most patients will at least have gr 1 dermatitis. We will keep a record of toxicity at each visit by collecting the Lent Soma evaluation of

the clinician at each visit after treatment starts. Patient reported fatigue rate will not be collected on the adverse event report, but will also be recorded at each visit

Total Patients	Upper limit of number of patients with toxicity for the trial to continue	Proportion of patients with toxicity if exceed the upper limit	Lower limit of 95% Cl	Upper Limit of 95% CI
3	<3	100%	29%	100%
4	<4	100%	40%	100%
5	<4	80%	28%	99%
6	<4	67%	22%	96%
7	<5	71%	29%	96%
8	<5	63%	24%	91%
9	<5	56%	21%	86%
10	<6	60%	26%	88%
11	<6	55%	23%	93%
12	<6	50%	21%	79%
13-50	<7	>20%	NA	

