**Study Cohort and Definition**

1. Concurrent vs. Neoadjuvant
  - a. Concurrent: ADT <= 30 days leading up or within 2 weeks after the RT start date.
  - b. Neoadjuvant: ADT >30 day leading up RT start date.
2. Toxicity Grade Scale  
Grade 1: Mild or pain does not interfere with activity

Grade 2: Moderate or repeated use of nonnarcotic pain reliever > 24 hours or interferes with activity

Grade 3: Severe or any use of narcotic pain reliever or prevents daily activity

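### The primary skin-toxicity rate is defined on NCI-CTC v3 Grade 3, but the SAP plans no such rate and its only toxicity scale draws Grade 3 elsewhere, so the count could be misclassified in either direction

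*Protocol*

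**What the plan says.** **Protocol, Primary Outcome Measure.** "Cutaneous toxicity rate will be assessed by the National Cancer Institute Common Toxicity Criteria (NCI-CTC) v 3. grading scale".

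**Protocol, Monitoring Plan for Severe Adverse Events.** The hypothesis is that "a maximum of 20% of patients might experience severe acute skin side effects". Severe is set equal to NCI-CTC Grade 3, and the plan adds: "This corresponds to symptoms interfering with activities of daily life". The monitoring board suspends the protocol if "more than 16 of 80 patients demonstrate severe acute skin toxicity". Skin adverse events are collected, with grade 1 and 2 dermatitis left off the report. The section then says: "We will keep a record of toxicity at each visit by collecting the Lent Soma evaluation".

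**Protocol, Data Collection.** A clinician assesses cutaneous toxicity at every visit after baseline, but no scale is named for that assessment. The same section adds: "The objective LENT SOMA questionnaire Part 3 will be completed by a study clinician or trained nurse at each visit after baseline".

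**Protocol, Patients Requiring Regional Nodal Irradiation.** This cohort has its own 20% rule for Grade 3 skin toxicity, with no scale named. Grade 3 brachial plexopathy in the same section is defined on LENT/SOMA or RTOG.

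**SAP, Study Cohort and Definition.** The only toxicity scale is worded around pain and analgesic use. Its middle grade reads: "Grade 2: Moderate or repeated use of nonnarcotic pain reliever > 24 hours or interferes with activity". Its Grade 3 is severe, or any narcotic analgesic use, or symptoms that stop daily activity.

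**SAP, Outcome and definition.** The outcomes are skin thickening ratio (baseline, one year and change), overall survival, and local and distant recurrence-free survival. No graded skin toxicity rate is listed.

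**The concern.** The primary safety question is whether the Grade 3 skin rate stays within 20%. That comparison means something only if the observed rate is graded on the scale on which the 20% was set. Interference with daily life marks Grade 3 in the protocol, while interference with activity marks Grade 2 in the SAP. The SAP also makes narcotic use sufficient for Grade 3, which the protocol's description does not mention. The graded clinician instrument that the protocol names for each visit is a third scale, LENT SOMA, and neither document links it to NCI-CTC.

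An analyst working from the SAP therefore has no instruction to produce the NCI-CTC rate and one toxicity scale that would give a different count. At stake is whether the reported primary rate can be read against the protocol's own limit.

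**Working it through.** **1. The plan's own figure.** 16/80 = 20.0%, which matches the stated maximum. The first count above it is 17/80 = 21.25%. The limit is consistent with the hypothesis; the question is what is counted.

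**2. The definitions side by side.**

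| Feature | Protocol (NCI-CTC v3, as described there) | SAP scale |
|---|---|---|
| Symptoms interfere with activity | Grade 3 | Grade 2 |
| Symptoms stop daily activity | not separated | Grade 3 |
| Any narcotic analgesic use | not mentioned | Grade 3 |
| Judged severe | Grade 3 | Grade 3 |
| Tied to skin | yes | not stated |
| Tied to the 20% limit | yes | no |

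The first row can move patients down a grade and the third can move patients up. The fourth can leave a patient where she was. The net direction cannot be read from the text.

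**3. How much regrading would matter.** The documents give no share of patients who would change grade, so the shares below are assumptions. The test is the chance of more than 16 events in 80, P(X ≥ 17) with X binomial(80, q). This is a single look at 80 patients; the protocol's continuous monitoring table is not modelled.

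*Downward.* If a share f of true Grade 3 cases is recorded as Grade 2, q = p(1 − f). For example, 0.30 × (1 − 0.25) = 0.225 and 80 × 0.225 = 18.

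| True rate p | f | Expected in 80 | P(more than 16) |
|---|---|---|---|
| 25% | 0 / 25% / 50% | 20 / 15 / 10 | 0.816 / 0.325 / 0.019 |
| 30% | 0 / 25% / 50% | 24 / 18 / 12 | 0.970 / 0.648 / 0.084 |

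*Upward.* If a share g of the other patients is recorded as Grade 3 through narcotic use, q = p + (1 − p)g. For example, 0.15 + 0.85 × 0.05 = 0.1925 and 80 × 0.1925 = 15.4.

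| True rate p | g | Expected in 80 | P(more than 16) |
|---|---|---|---|
| 10% | 0 / 5% / 10% | 8 / 11.6 / 15.2 | 0.002 / 0.065 / 0.346 |
| 15% | 0 / 5% / 10% | 12 / 15.4 / 18.8 | 0.084 / 0.368 / 0.723 |

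*Both at once.* The shifts cancel when p × f = (1 − p) × g. At p = 20%, f = 20% and g = 5% give 0.20 × 0.20 = 0.80 × 0.05 = 0.04. The rate is then unchanged, but different patients are counted as severe.

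**4. LENT SOMA.** Without a conversion rule in either document, no calculation can say how a LENT SOMA Grade 3 count relates to an NCI-CTC Grade 3 count.

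**The case against.** The strongest reply is that nothing in the documents requires the primary count to be taken from the wrong scale.

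- The SAP scale appears among cohort definitions, next to a rule on concurrent versus neoadjuvant ADT. It is not attached to skin, to any outcome or to the 20% limit.
- The SAP is dated 04/01/2021, is written in the past tense and reports 75 included cases. It is not the monitoring document. The main skin limit is stated on NCI-CTC Grade 3, so a reader who infers that the monitoring board counted on the SAP's pain scale goes beyond the text.
- The LENT SOMA sentence follows directly after the one that leaves grade 1 and 2 dermatitis off the adverse event report. It reads most naturally as an additional record, not as a replacement for NCI-CTC. Grade 3 skin events still have the adverse event route and the clinician's assessment.
- The SAP's Grade 3 includes severe, which is also the protocol's word for its own Grade 3.

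All of this stands, and it limits the point to what could happen. It does not remove it. The adverse event section names no scale for its grade 1 and 2 cut-off, so that route depends on the same unanswered question. And if the SAP scale was never meant for skin, the SAP has no grading rule and no planned rate for the protocol's primary cutaneous outcome. Either reading needs a correction.

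**Conclusion.** The point holds in a limited form. The protocol fixes the primary cutaneous rate, the 20% limit and the count of 16 in 80 on NCI-CTC v3 Grade 3. The SAP lists no such rate and contains one toxicity scale, whose Grade 3 boundary lies elsewhere. The visit record is LENT SOMA with no conversion, and the nodal cohort's skin rule names no scale. If the SAP scale or the LENT SOMA records are used for the primary count, Grade 3 could be misclassified in either direction and the result could not be compared with 20%.

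Two stronger readings are tempting and are not supported. A reader might infer that severe toxicity will be miscounted, and specifically undercounted. The documents show neither, because a correct count remains possible and the SAP wording can also move patients up. A reader might also infer that the conclusion against 20% would reverse. The tables above show that it could, but only under assumed true rates and assumed shares; the actual size cannot be derived from the documents.

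**What to change.** Reconcile the sections as follows.

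1. State in the SAP that the primary cutaneous rate is the proportion of patients with NCI-CTC v3 skin toxicity of Grade 3 or higher.
2. Name the source record: the clinician's skin assessment at each visit after baseline, together with the adverse event report.
3. Name that same scale for both skin stopping counts, including the one in the regional nodal cohort.
4. Replace the SAP's present scale for this outcome, or restrict it explicitly to pain.
5. Report the LENT SOMA results as secondary.

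The cost is mainly wording. Because the SAP was written after the data were assembled, some visits may have no NCI-CTC grade. Those grades should be taken from clinical notes and adverse event reports. Photographs alone will not do, since they cannot show whether symptoms interfered with daily life. The number of visits that cannot be graded should be reported beside the rate.

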# Patients Requiring Regional Nodal Irradiation

Among patients requiring regional nodal irradiation, we hypothesize that <3.0% of patients will develop severe brachial plexopathy following radiation to the regional nodes defined as LENT/SOMA or RTOG Grade 3 or higher (Continuous paresthesias with incomplete motor paresis; pain medication is generally required or objective neurologic findings with paresthesia or paresis) As this toxicity occurs after radiation treatment is complete, patients will be formally assessed for brachial plexopathy at baseline and at 7-12 weeks and 12-18 months post radiation for comparison with baseline assessments. However, patients will be asked to contact [name] if symptoms of brachial plexopathy develop in between or after study visits. We also hypothesize that less than 15% of patients receiving regional nodal irradiation will develop 20% or greater increase in arm lymphedema (compared to baseline measurements) assessed at 7-12 weeks and 12-18 months post radiation. Of note, lymphedema that develops in the context of weight gain (>/=15% increase in weight) or trauma to the arm will not be attributed to the radiation treatment itself and will not be considered an event to due to the treatment. If this side effect is secondary to radiation rather than surgery, it generally occurs after radiation is complete. Lymphedema that takes place during the 3 weeks of radiation or before radiation begins will be attributed to surgery. During the study, the patients

will be monitored throughout the study such that if at any time during the study the upper limit of the number of patients receiving regional nodal irradiation developing Grade 3 brachial plexopathy or 20% or greater increase in arm lymphedema exceed the number just described or more than 20% develop grade 3 skin toxicity within the breast or chest wall, the trial will be discontinued to the patients requiring regional nodal irradiation but may remain open to patients who do not require regional nodal irradiation. For patients requiring regional nodal irradiation, we will only collect adverse events related to brachial plexopathy, lymphedema, skin toxicity, lung toxicity, heart toxicity. We will not report grade 1-2 radiation dermatitis as adverse events because most patients will at least have gr 1 dermatitis. We will keep a record of toxicity at each visit by collecting the Lent Soma evaluation of the clinician at each visit after treatment starts. Patient reported fatigue rate will not be collected on the adverse event report, but will also be recorded at each visit.

Stopping rule for monitoring 3 types of toxicities in patients Receiving Regional Nodal Irradiation.

Total Patients	Upper limit of number of patients with Grade 3 brachial plexopathy (<3%)	Upper limit of number of patients with 20% or greater increase in arm lymphedema (<15%)	Upper limit of number of patients with grade 3 skin toxicity within the breast or chest wall (<20%)
3	<2	<3	<3
4	<2	<3	<4
5	<2	<4	<4
6	<2	<4	<4
7	<2	<4	<5
8	<2	<4	<5
9	<2	<5	<5
10	<2	<5	<6
11	<2	<5	<6
12	<2	<5	<6
13-30	<2	<5	<7

(If any one of the 3 stopping rules is met, the trial stops for excessive toxicity.)

**Correlative Studies**: Blood will be analyzed for inflammatory markers (TNF-alpha, soluble sTNFR2, IL-6, IL-1ra, and CRP) to determine if they are associated with development of cutaneous toxicity. By acquiring the objective UTC measurements at 5 time points, the development and resolution of cutaneous toxicity as it relates to time may be further understood.

A description of the Feasibility:

There is no drug in the proposed study. Our department has 7 linear accelerators all capable of delivering hypofractionated external beam radiotherapy. We also have extensive experience treating patients with simultaneous integrated boost radiotherapy. As determined by 2000 census, the majority of minorities in our community are African American, and African Americans make up 61.4% of the population of metropolitan Atlanta. A study including this population would be feasible. At the three Emory radiation centers, there are approximately 350 patients seen annually with 200 patients having early stage breast cancer. With approximately 80 African American breast cancer with Stage 0-II patients treated annually at Emory Clifton Campus, Emory Midtown, and Grady Memorial Hospital. In a recent study, over 60% of our patients had breast separation >25cm. [17] This trial should be able to accrue 33 high risk patients (2 to 3 patients per month, and assuming a 10% dropout rate) needed to assess the feasibility of this novel hypofractionated simultaneous integrated boost (SIB) regimen.

[name] (co-PI) is an NIH funded physicist with expertise in ultrasound tissue characterization (UTC) of radiation induced cutaneous toxicity. [name] Imaging Laboratory is fully equipped with three clinical ultrasound machines including a state-of-the art Sonix RP scanner with raw radiofrequency echo signals and advanced research interface. The laboratory is located on the tunnel level within the Department of Radiation Oncology. It comprises 500 sq. ft. and is equipped with ultrasound data acquisition system and calibration targets. UTC measurements will be easily performed in patients using [name] equipment and software. Measurements of breast tissue take about 10 minutes to complete.

The MFI, PSS, PSQI, IDS-SR, SF-36 and GLTEQ, and LENT SOMA are surveys which have been validated in various populations and take 15 minutes to complete in total.

Blood for inflammatory markers is routinely processed within the laboratory of my research mentor, [name], Professor of Psychiatry and an international expert on inflammatory induced behavioral changes. He has agreed to help process the blood from this study.

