Information regarding disease characteristics (including stage, tumor size, grade), patient demographics (including age, race, co-morbidities, social history, body mass index), systemic treatment (including hormone therapy, systemic therapy), surgical treatment, radiation treatment, and clinical outcomes (local control, distant metastasis, survival, and treatment complications) will be collected and recorded.

Patients may also be asked to participate in a long term assessment between 1 and 10 years where they will complete the same study procedures as outlined above. Patients will be compensated \$50.00 for completing this visit.

A follow up phone survey will be taken between 18 months and 10 years after treatment. Using the same scales as in the study visits, the patients will be asked to rate their fatigue level, breast pain, how happy they are with the look of their breast and how different their radiated breast is from their non-radiated breast. They will also be asked if they are on any hormonal treatment for breast cancer and if so, the date they started. We will obtain verbal consent for this survey from patients who completed this study before the follow up phone survey was originally approved on 9/24/2013.

Assuming 10% of patients dropout, 53 patients requiring breast only radiation will be enrolled (2-3 patients per month) to yield a total of 50 patients.

An additional 33 patients requiring regional nodal irradiation and breast or chest wall radiation will be enrolled. Assuming 10% of patients dropout, 33 patients of these patients will be enrolled (2-3 patients per month) to yield a total of 30 patients receiving regional nodal irradiation and breast or chest wall radiation.

In patients undergoing regional nodal irradiation, arm measurements will be taken of the ipsilateral and contralateral upper extremity at baseline, 7 - 12 weeks, and 12 – 18 months post XRT by a licensed lymphedema therapist or study staff trained by a licensed lymphedema therapist. These patients will also be assessed for brachial plexopathy using RTOG grading toxicity, LENT/SOMA grading toxicity, and a modified version of a validated questionnaire to assess symptoms of brachial plexopathy at baseline and 7 - 12 weeks, and 12 – 18 months post XRT.[24] If a patient develops RTOG or LENT/SOMA Grade 3 toxicity, an objective measurement (MRI and/or nerve conduction studies) of brachial plexopathy will be employed.

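### Lymphedema exclusions for weight, trauma and onset appear in one protocol section but not in the primary outcome, and a weight cut-off stands in for the contralateral-arm comparison that the scheduled data allow

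*Protocol*

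**What the plan says.** The protocol describes the lymphedema event in three places.

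- Primary Outcome Measure: "Rate of 20% or greater increase in arm lymphedema (compared to baseline arm measurements) will be assessed" among patients receiving regional nodal irradiation. No exclusion is attached.
- Patients Requiring Regional Nodal Irradiation, hypothesis text: "less than 15% of patients receiving regional nodal irradiation will develop 20% or greater increase in arm lymphedema (compared to baseline measurements". The two assessment points are 7-12 weeks and 12-18 months. Exclusions follow: "lymphedema that develops in the context of weight gain (>/=15% increase in weight) or trauma to the arm will not be attributed to the radiation", and such a case "will not be considered an event to due to the treatment". On timing: "Lymphedema that takes place during the 3 weeks of radiation or before radiation begins will be attributed to surgery".
- The nodal stopping table in the same section: the column limit is the number of patients with a 20% or greater increase, headed <15%. The exclusions are not repeated. The limit is <5 from 9 to 30 patients.

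On measurement, the Data Collection section says that "arm measurements will be taken of the ipsilateral and contralateral upper extremity at baseline, 7 - 12 weeks" and again at 12-18 months. These are three of the five regular visits. Arms are not scheduled for measurement at fraction 15 or at 2-5 weeks. No section says how the contralateral arm enters the event. The SAP does not list lymphedema among its outcomes, so it does not settle the definition.

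**The concern.** The same primary outcome can be read with or without the exclusions, and both a 15% hypothesis and a stopping limit depend on it. Every exclusion works in one direction: it removes a case that the Primary Outcome Measure section would count.

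The weight rule is also a crude tool. Just under a 15% gain, the increase over baseline is taken as it stands. At 15% the event is cancelled, however large the swelling. Weight loss, which can hide swelling, is not mentioned. The other arm, measured on the same day, gives a direct correction for general change in limb size.

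The timing rule rests on thin evidence. No arm measurement is scheduled between baseline and 7-12 weeks, so onset during the three weeks of radiation depends on unscheduled observation. Swelling that starts then and is still present at 7-12 weeks has no stated handling. No denominator rule or adjudicator is given for patients with a discounted event.

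**Working it through.** **Inputs from the protocol.** 30 evaluable nodal patients (33 enrolled, 10% dropout), a 15% hypothesis, a 20% increase as the event, and stopping limits of <3 at n = 3-4, <4 at n = 5-8 and <5 at n = 9-30. The share of events that would be excluded is not given, so a range of 0 to 50% is assumed.

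**Step 1: the plan's own figures.** 30 × 1.10 = 33 matches the stated enrolment; 30/0.90 = 33.3, or 34 rounded up, is close to it. For n = 3 to 12, take the smallest count whose exact two-sided 95% lower confidence limit exceeds 15%. All ten rows of the lymphedema column reproduce. For example, 4 of 8 has a lower limit of 15.7% and 3 of 8 has 8.5%; 5 of 12 has 15.2% and 4 of 12 has 9.9%. From n = 13 this rule no longer gives the limit (5 of 13 has a lower limit of 13.9%). The limit of <5 then agrees with the point estimate at 30 patients.

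**Step 2: what one event does.** 1/30 = 3.3 percentage points.

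| All events | Excluded | All / 30 | Counted / 30 | Counted / (30 − excluded) |
|---|---|---|---|---|
| 5 | 1 | 16.7% | 4/30 = 13.3% | 4/29 = 13.8% |
| 6 | 2 | 20.0% | 4/30 = 13.3% | 4/28 = 14.3% |

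In both rows the exclusions move the result from above 15% to below it, and from reaching the limit to not reaching it.

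**Step 3: range over the unknown share.** Let p be the all-cause rate and f the excluded share. The counted rate is q = p(1 − f), and P(at least 5 of 30) = 1 − Σ C(30,k) q^k (1 − q)^(30−k) for k = 0 to 4.

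| p | f = 0 | 10% | 20% | 30% | 50% |
|---|---|---|---|---|---|
| 15% | 47.6% | 38.1% | 28.8% | 20.2% | 7.0% |
| 20% | 74.5% | 64.9% | 53.7% | 41.3% | 17.5% |
| 25% | 90.2% | 83.7% | 74.5% | 62.2% | 31.9% |
| 30% | 97.0% | 93.7% | 87.9% | 78.5% | 47.6% |

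Applying the limits sequentially from n = 3 changes these by at most about 0.2 points. The share that brings the counted rate down to 15% is 1 − 0.15/p: 25% at p = 20%, 40% at p = 25% and 50% at p = 30%.

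**Step 4: weight.** Assume, for illustration only, that weight change scales both arms by a factor g and that swelling multiplies the ipsilateral arm by (1 + s). A change from baseline in the ipsilateral arm is g(1 + s), so the event needs 1 + s ≥ 1.20/g.

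- 14% gain: 1.20/1.14 = 1.053, so about 5% true swelling is enough.
- 10% loss: 1.20/0.90 = 1.333, so about 33% is needed.
- 15% gain or more: no amount of swelling counts.

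In the inter-arm ratio, (ipsilateral/contralateral at follow-up) ÷ (the same at baseline) = g(1 + s)/g = 1 + s. The weight factor cancels and the 20% threshold keeps one meaning for every patient.

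**The case against.** The strongest reply is that the protocol wants swelling caused by radiation. For that target, removing true trauma or weight events is correct, and counting them in a study without a control group would charge surgical and accidental swelling to radiation. The rules are written in advance, the weight rule has a numeric cut-off, and the timing rule has a stated reason. This stands: all-cause versus attributed is a choice of estimand, and the all-cause rate need not be the only primary figure.

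A reader might infer that the lymphedema rate is simply biased low. The documents do not support that. It is lower only relative to the outcome as the Primary Outcome Measure section lists it. For a strictly radiation-attributable rate, uncorrected gain below 15% can raise the count and ignored weight loss can lower it, so the net direction is undetermined.

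Two further inferences go too far. The contralateral arm is not measured at every visit, only at three of five, although these include baseline and both lymphedema assessments. Nor is onset during radiation wholly uncheckable: lymphedema adverse events are collected and a clinician evaluation is recorded at each visit after treatment starts. What is missing is a scheduled arm measurement.

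It can also be said that the text never limits the comparison to the ipsilateral arm, and that the stopping table, in the same section as the exclusions, may be meant to inherit them. Both readings are open. But a weight exclusion would have little purpose if the arms were already being compared, and an unstated inheritance is itself what needs reconciling.

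**Conclusion.** The concern holds in a limited form. The primary outcome as listed and the nodal section disagree on which lymphedema cases count, and the stopping table does not say which it follows. The exclusions cannot raise the counted rate above the listed primary outcome, and may lower it.

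How much is unknown. If no patient has a 15% weight gain, arm trauma or onset before or during radiation, the effect is nil. With 30 patients, one reclassified event is enough to change the reading. At an assumed all-cause rate of 20%, the chance of reaching five counted events falls from 74.5% with none excluded to 53.7% if a fifth are. These figures assume independent patients, all 30 evaluable, and the assumed shares shown. The weight illustration also assumes that both arms scale alike with weight.

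Separately, a better measure than the weight cut-off is available from measurements already scheduled.

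**What to change.** 1. Define the event as the ipsilateral/contralateral ratio at 7-12 weeks or 12-18 months, divided by the same ratio at baseline, being at least 1.20, on one named arm measure. Drop the 15% weight-gain exclusion, which this replaces.
2. Report the rate of all such events beside the rate after the trauma and onset attributions. Keep patients with a discounted event in the denominator of both.
3. State who decides attribution, what record of trauma and onset date is used, and how swelling that begins during radiation and persists to 7-12 weeks is handled.
4. Reconcile the Primary Outcome Measure section, the nodal hypothesis text and the stopping table on which count is compared with 15% and which with the stopping limit.
5. Add lymphedema to the SAP outcomes.

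The cost is wording and, since the SAP is written in the past tense, probably a reanalysis. The ratio needs no measurement beyond the three scheduled for both arms, and no follow-up weight. The attributed rate needs trauma and onset records, for which the protocol sets no schedule. The ratio corrects for weight only, not for trauma or timing of onset, and the reported rate may look slightly less favourable.
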